12.2.3.3 Summary of Best overall RECIST Response (BoR) and ORR

For each treatment arm, best overall response (BoR) will be summarised by n (%) for each category (CR, PR, SD, PD, NE). No formal statistical analyses are planned.

The objective response rate (ORR) will be summarised (i.e., number of patients (%)) by treatment group.

ORR and BOR will be presented based on the BICR data and also the investigator recorded data.

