Subgroup analyses will be conducted to assess consistency of treatment effect across potential or expected prognostic factors (see Section 12.2.2 for all predefined subgroups). An analysis will not be performed if there are too few events available for a meaningful analysis of a particular subgroup (i.e., if there are less than 20 events in a subgroup)..

A further analysis of OS and PFS2 will be performed when the OS data are approximately 60% mature (~190 events) and a multiplicity adjustment will be made to account for the different analyses.

Supportive analyses of time to subsequent therapy or death, and time to second subsequent therapy or death will be provided, using the same methodology as specified for the primary

analyses of PFS; however no multiplicity adjustment will be applied as these are viewed as supportive endpoints.

Objective tumour response rates (based on central review) will be summarised for the two treatment arms. In addition, the investigator reported response rates will also be summarised.

Exploratory analyses of OS which attempt to adjust for any potential confounding impact of subsequent use of PARP inhibitors on the control arm may be performed if an appropriate proportion of patient's on the control arm receive such treatments and sufficient information is collected on subsequent therapy use. Methods such as Rank Preserving Structural Failure Time (RPSFT) (Robins et al 1991), Inverse Probability of Censoring Weighting (IPCW) (Robins 1993) and other methods in development will be explored. The decision to adjust and final choice of methods will be based on a blinded review of the data and the plausibility of the underlying assumptions. Other subsequent therapies may also be considered such as platinum therapies if important imbalances are reported across the treatment arms. Details will be pre-specified in the SAP or Payer Analysis Plan as this analysis is intended to support reimbursement appraisals.

Analysis of Patient Reported Outcomes (PRO) endpoints

Descriptive statistics will include means, standard deviations, medians, and ranges for each continuous or ordinal scale/subscale/item by arm at each time point. Descriptive graphical techniques will include mean plots by arm for each continuous or ordinal scale/subscale/item. Relative frequencies of responses for each ordinal item will also be generated at each time point by arm.

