2.2 Secondary objectives

The secondary objectives of this study are:

1. To compare the efficacy of single agent olaparib versus physician's choice chemotherapy (capecitabine, vinorelbine or eribulin) by assessment of overall survival, time to second progression or death (PFS2) and objective response rate (ORR) using BICR data assessed by RECIST 1.1.
2. To assess the effect of olaparib on the Health-related Quality of Life (HRQoL) as measured by EORTC QLQ-C30 global QoL scale.
3. To assess efficacy of olaparib in patients identified as having a deleterious or suspected deleterious variant in either of the *BRCA* genes using variants identified with current and future *BRCA* mutation assays (gene sequencing and large rearrangement analysis).
4. To determine the exposure to olaparib in patients receiving olaparib monotherapy

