12.2 Methods of statistical analyses

The treatment comparison is olaparib 300 mg bid vs physician's choice of chemotherapy.

Results of all statistical analysis will be presented using a 95% confidence interval and 2-sided p-value.

The following table details which endpoints are to be subject to formal statistical analysis, together with pre-planned sensitivity analyses making clear which analysis is regarded as primary for that endpoint

Table 10 Formal Statistical Analyses to be Conducted and Pre-Planned Sensitivity Analyses

Endpoints Analysed	Notes
PFS (Time from randomisation to first progression or death)	Primary analysis stratified log-rank test using BICR data
	Sensitivity/supportive analyses ^a :
	1) Evaluation time bias analysis; stratified log-rank test using BICR data
	2) Attrition bias analysis (using alternative censoring rules); stratified log-rank test using BICR data
	3) Ascertainment bias analysis; stratified log-rank test using Investigator data
	4) Deviation bias (if meaningful to do); stratified log-rank test using BICR data
	5) Stratified log rank test of time from randomisation to first subsequent therapy or death 6) stratified log rank test using BICR data in randomised patients confirmed as BRCA mutation positive by central Myraid test (if applicable)
Overall Survival (Time from randomisation to death due to any cause)	Primary analysis: stratified log-rank test Supportive analysis: KM plot of time to censoring for OS
PFS2 (Time from randomisation to second progression or death)	Primary analysis: Stratified log rank test based on investigator assessment of second progression Supportive analysis: Stratified log rank test of time from randomisation to second subsequent therapy or death
Objective Response Rate (Number of patients who have a CR or PR determined using RECIST 1.1 criteria divided by the number of patients with measurable disease.)	Primary: ORR per treatment arm (descriptive only) based on BICR data Supportive: ORR per treatment arm (descriptive only) based on investigator assessment

Table 10 Formal Statistical Analyses to be Conducted and Pre-Planned Sensitivity Analyses

Endpoints Analysed	Notes
Adjusted mean change from baseline in global QoL score from the EORTC QLQ-C30 questionnaire	Primary analysis: mixed model for repeated measures (MMRM) analysis of all of the post-baseline scores for each visit

^a See Section 12.2.2.1 for further details

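### Secondary objective 1 sets out to compare the arms on ORR, but the plan gives ORR by arm only, with no between-arm estimate, confidence interval or stratification-adjusted contrast

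*Protocol*

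**What the plan says.** Protocol section 2.2 (and the synopsis) words secondary objective 1 as "To compare the efficacy of single agent olaparib versus physician's choice chemotherapy", with OS, PFS2 and "objective response rate (ORR) using BICR data assessed by RECIST 1.1" as the three measures.

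The analysis text for ORR is as follows.

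- Synopsis, statistical methods: "Objective tumour response rates (based on central review) will be summarised for the two treatment arms".
- Section 12.2, Table 10, the table of formal and sensitivity analyses: "Primary: ORR per treatment arm (descriptive only) based on BICR data" and "Supportive: ORR per treatment arm (descriptive only) based on investigator assessment".
- Section 12.2.3.3: the best-response paragraph ends "No formal statistical analyses are planned". The next paragraph gives ORR as a number and percentage of patients by treatment group.

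The denominator is stated in more than one way. Sections 11.1.2.3 and 12.1.3 and Table 10 use patients with measurable disease at baseline, the evaluable-for-response (EFR) set. Table 9 puts ORR under the full analysis set, and section 12.1.1 assigns all efficacy data to that set.

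**The concern.** OS and PFS2, named in the same sentence of the same objective, each get a stratified log-rank test and a hazard ratio with confidence interval. ORR gets no treatment-effect estimate at all. This is not silence to be filled by the SAP: the protocol itself fixes ORR as descriptive, so a SAP that added a contrast would depart from Table 10.

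Section 3.2.1 counts BICR ORR among the secondary endpoints meant to give further support for clinical benefit. With 2:1 allocation the control rate rests on about 103 patients at most, and on fewer once those without measurable disease are left out. At that size an apparent gap needs an interval beside it, and the stratification used at randomisation should be reflected in the estimate.

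**Working it through.** **Plan's own figures.** The protocol gives no design figure for ORR. Its PFS figure reproduces. With allocation 2/3 : 1/3 and HR 0.635, events = (1.960 + 1.282)² / [(2/3)(1/3)(ln 0.635)²], which gives 230. Power at 230 events is 90.1%. ORR is therefore the part of the plan that needs looking at, not the sample size.

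**What each endpoint receives.**

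| Endpoint | In multiple testing procedure | Between-arm output |
|---|---|---|
| OS, PFS2 (secondary objective 1) | Yes | Stratified log-rank, HR, 95% CI |
| ORR (secondary objective 1) | No | None; n (%) by arm |
| Global QoL (secondary objective 2) | No | Difference, 95% CI, p-value (12.2.3.4) |
| Time to first subsequent therapy or death (supportive) | No | HR, 95% CI (12.2.2.1) |
| Time to second subsequent therapy or death (supportive) | No | HR, 95% CI (12.2.3.1) |

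Standing outside the multiple testing procedure does not stop the plan from giving an effect estimate elsewhere.

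**Illustration of what an interval would show.** Inputs:

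- From section 12.3: 310 patients at 2:1, so 310 × 2/3 ≈ 207 and 310 × 1/3 ≈ 103.
- Assumed: 70% to 100% with measurable disease, and control ORR 20% to 30%.
- Olaparib ORR 41%: the 400 mg bid capsule group, 11/27, section 1.1.6.1. The other breast cancer figures there are 6/27 (22%), 0 of 26 and 8/62 (12.9%), in differing doses and populations. A 30% case is added as an assumed lower value.

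Formulas: 95% half-width for the difference = 1.96 × √[pT(1−pT)/nT + pC(1−pC)/nC]. The odds ratio interval uses the standard error √[1/a + 1/b + 1/c + 1/d] on the log scale, where a to d are the four cell counts.

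At 80% measurable (165 vs 83), 41% vs 25%: √[0.2419/165 + 0.1875/83] = √0.003725 = 0.0610, and × 1.96 = 0.120.

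| Olaparib vs control | Difference (95% CI), points | Odds ratio (95% CI) |
|---|---|---|
| 41% vs 20% | 21 (10 to 32) | 2.78 (1.49 to 5.17) |
| 41% vs 25% | 16 (4 to 28) | 2.08 (1.16 to 3.74) |
| 41% vs 30% | 11 (-1 to 23) | 1.62 (0.92 to 2.85) |
| 30% vs 20% | 10 (-1 to 21) | 1.71 (0.91 to 3.23) |

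Across 70% to 100% measurable (145 vs 72 up to 207 vs 103) and these rates, the half-width is about 10 to 13 points.

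**Why the denominator must be settled.** Section 11.1.2.3 lets only patients with measurable disease count as responders. If 80% are measurable in each arm, 41% vs 25% in the EFR set becomes 0.8 × 41 = 32.8% vs 0.8 × 25 = 20.0% in the full analysis set. The difference falls from 16 to 12.8 points.

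**The case against.** The synopsis, Table 10, section 12.2.3.3 and the multiplicity section all treat ORR as a descriptive endpoint, so the choice looks deliberate. The conflict comes down to one verb in the objective, and rewording the objective would also remove it. That is fair, but rewording would give up an estimate that the data already support, while endpoints of lower standing keep theirs.

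A reader might infer that the trial cannot answer the ORR part of its objective at all. The documents do not support that. Counts by arm over a defined denominator allow a crude difference or odds ratio with an interval, and the illustration above uses nothing more. What cannot be recovered from those counts is the version adjusted for the stratification factors, or a contrast that the protocol has committed to.

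A reader might also take "No formal statistical analyses are planned" as ruling out an ORR analysis by itself. It closes the best-response paragraph, and ORR follows separately, so Table 10 is the governing text. The general rule "Results of all statistical analysis will be presented using a 95% confidence interval and 2-sided p-value" does not fill the gap, since an endpoint marked descriptive falls outside it.

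Leaving ORR out of the multiple testing procedure, and stating no power for it, are legitimate choices and no part of this point.

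**Conclusion.** The point holds as a mismatch between a stated objective and a stated analysis: the objective says compare, and the plan specifies no between-arm ORR estimate, interval or stratified contrast. A crude contrast remains derivable, so the loss is limited to a planned, adjusted estimate with its uncertainty.

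The 10 to 13 point half-width is illustrative only. It rests on an assumed control ORR, an assumed measurable share and olaparib rates of 30% or 41%. Earlier breast cancer figures in the protocol run from 0% to 41%, so 41% sits at the top. The mismatch itself depends on none of these numbers.

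The primary PFS analysis, the testing of PFS2 and OS, type I error control and the sample size are unaffected. This should be corrected, but it does not threaten the trial's main conclusion.

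**What to change.** In Table 10 and section 12.2.3.3, add the BICR ORR odds ratio and/or difference, olaparib vs chemotherapy, with 95% CI, adjusted for the three randomisation stratification factors (logistic regression or a Cochran-Mantel-Haenszel estimate). Give the same estimate for investigator ORR as supportive. Label both nominal and outside the multiple testing procedure. Best-response categories can stay descriptive.

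State the denominator as the EFR set, correct the Table 9 entry for ORR, and add the matching exception to section 12.1.1. Because measurable disease is defined at baseline, the comparison within that set stays a randomised one.

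The three binary factors make 2 × 2 × 2 = 8 strata. With about 83 control patients (80% measurable, assumed) that averages about 10 controls per stratum, so the method should tolerate sparse strata.

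The cost is a wording change and one table, with no new data, patients or alpha. The small downside is one more nominal interval, which must be labelled as such.

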12.2.3.4 Analysis of PRO endpoints

HRQoL – Global score

The primary assessment of HRQoL will focus on comparing mean changes from baseline in the global QoL Score (from the EORTC QLQ-C30 questionnaire) between the treatment arms. The analysis population for mean changes in HRQoL data will be the FAS (ITT) set and will include all randomised patients with an evaluable baseline assessment and at least one evaluable post baseline assessment.

Change from baseline will be derived using a mixed model for repeated measures analysis of all of the post-baseline scores for each visit. Restricted maximum likelihood (REML) estimation will be used.

The model will include treatment, visit and treatment by visit interaction as explanatory variables and the baseline QoL score as a covariate. Treatment, visit and treatment by visit interaction will be fixed effects in the model. The treatment by visit interaction will remain in the model regardless of significance.

The adjusted mean change from baseline estimates and corresponding 95% confidence intervals will be presented by visit for each treatment group and corresponding plots over time will be presented.

Data will be descriptive and plots will be used to visualise the adjusted mean global QoL score across time for each treatment arm.

An overall adjusted mean estimate will also be derived that will estimate the average treatment effect over visits giving each visit equal weight. For this overall treatment comparison, adjusted mean estimates per treatment group and corresponding 95% confidence intervals will be presented along with an estimate of the treatment difference, 95% confidence interval and p-value.

In addition, summary tables of the overall responses in global QoL score for each visit (improvement, deterioration and no change) will be presented by treatment arm as well as the best overall response. Only patients who have a baseline global QoL scores ≥ 10 will be included in the summaries of overall visit response and best response.

HRQoL – additional item scores

To support the primary assessment of HRQoL other items of interest will be summarised.

Unadjusted mean changes from baseline and overall visit responses (including best overall response) will be summarised for the following multi-item functional sub-scales from the EORTC QLQ-C30:

- Physical
- Role
- Emotional
- Cognitive
- Social

These additional sub-scales are considered exploratory to support the primary HRQoL endpoint (global score) and assess if any observed differences are driven by particular domains of functioning, symptoms or group of symptoms.

The remaining symptom scale scores of the QLQ-C30 (fatigue, pain vomiting and nausea) will be summarised descriptively based on tables and plots of unadjusted mean change from baseline. Overall visit responses and best visit response will not be reported for these domains..

HRQoL questionnaire compliance overall and over time will be summarised by randomised treatment.

CTSQ

Data from the CTSQ-16 scores of treatment satisfaction (as measured by the Satisfaction with Therapy scale and the other sub-scales and items of the CTSQ-16) will be summarised and listed by treatment arm.

Compliance

Overall compliance will be defined as the number of patients who provided both a baseline and at least one post baseline assessment for which there were sufficient data recorded for the visit to be evaluable for the global QoL score, divided by the number of patients randomised. Compliance over time is calculated separately for each visit, including baseline, as the number of patients providing an evaluable assessment for the global QoL score at that visit divided by the number of patients expected to have provided an assessment.

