5.2.1 Procedures for randomisation

Patient eligibility will be established before treatment randomisation. Once the eligibility of a patient has been confirmed, the Investigator (or nominated assistant) should contact the IVRS/IWRS Centralised Randomisation Centre for allocation of randomised therapy. The investigator must declare prior to randomisation their choice of chemotherapy i.e. capecitabine or vinorelbine or eribulin.

The actual treatment given to individual patients will be determined by a randomisation scheme that has been loaded into the (IVRS/IWRS) database. The randomisation scheme will be produced by a computer software program called GRand (AZ Global Randomisation system) that incorporates a standard procedure for generating random numbers.

A blocked randomisation will be generated and all centres will use the same list in order to minimise any imbalance in the number of patients assigned to each treatment group.

The randomisation scheme will be stratified based on:

- Received prior chemotherapy regimens for metastatic breast cancer (yes/no)
- ER and/or PgR positive vs ER and PgR negative
- Prior platinum for breast cancer (yes/no)

For the purpose of stratification, a patient is considered to have received a chemotherapy regimen if he or she received at least 1 cycle of chemotherapy (at least 3 infusions if weekly regimen), or if he or she progressed clinically before completing a full cycle.

Patients will be identified to the Centralised Randomisation Centre using patient E-code and date of birth.

Randomisation codes will be assigned strictly sequentially as patients become eligible for randomisation.

Eligible patients will be randomised in a 2:1 ratio as specified below:

- olaparib tablets po 300 mg twice daily
- physician's choice of chemotherapy
 - Capecitabine 2500 mg/m² po daily (divided in 2 doses) x 14 days, repeat every 21 days
 - Vinorelbine 30 mg/m² IV Day 1 and Day 8, repeat every 21 days
 - Eribulin mesylate 1.4 mg/m² or Eribulin (active substance) 1.23mg/m² IV Day 1 and Day 8, repeat every 21 days

It is recommended that patients commence study treatment as soon as possible after randomisation, and ideally within 3 days.

5.3 Procedures for handling patients incorrectly enrolled or randomised or initiated on study treatment

Patients who fail to meet the inclusion/exclusion criteria should not, under any circumstances, be enrolled or receive study treatment. There can be no exceptions to this rule.

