12.2.2 Analysis of primary endpoint

PFS will be analysed when approximately 230 progression events have occurred, based on the BICR data. No further analyses of PFS are planned beyond this point unless requested by Health Authorities.

PFS will be analysed using a log rank test stratified by the stratification factors. The hazard ratio (HR) and confidence interval will be estimated from the U and V statistics obtained directly from the LIFETEST model with inclusion of STRATA terms for the stratification variables (and using the Breslow approach for handling ties).

The HR and its confidence interval will be estimated from the log-rank as follows ([Berry et al 1999](#) and [Sellke et al 1983](#))

$$\text{HR} = \exp(U/V)$$

$$95\% \text{ CI for HR} = (\exp\{U/V - 1.96/\sqrt{V}\}, \exp\{U/V + 1.96/\sqrt{V}\})$$

Where $U = \sum_i (d_{1i} - e_{1i})$ is the log-rank test statistic (with d_{1i} and e_{1i} the observed and expected events in group 1) and \sqrt{V} the standard deviation of the log-rank test statistic as produced in the LIFETEST output.

The HR (olaparib vs chemotherapy) together with its corresponding 95% confidence interval (CI) and p-value will be presented (a HR less than 1 will favour olaparib).

Stratification variables will be defined according to data from the interactive voice/web response system (IVRS/IWRS). If there are any patients who were mis-stratified, a sensitivity analysis will be carried out using the (correct) baseline data collected in the eCRF.

A Kaplan-Meier (KM) plot of PFS will be presented by treatment group. Summaries of the number and percentage of patients experiencing a PFS event, and the type of event (RECIST or death) will be provided along with median PFS for each treatment arm.

The assumption of proportionality will be assessed. Note that in the presence of non-proportionality, the HR will be interpreted as an average HR over the observed extent of follow-up. Proportionality will be tested firstly by producing plots of complementary log-log (event times) versus log (time) and, if these raise concerns, a time dependent covariate would be fitted to assess the extent to which this represents random variation.

The primary analysis will be based on the programmatically derived PFS based on BICR assessments, and using all scans regardless of whether they were scheduled or not.

The estimated PFS rates at 6 months and 12 months will be summarised (using the KM curve) and presented by treatment group.

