The number of patients prematurely censored will be summarised by treatment arm together with baseline prognostic factors of the prematurely censored patients. A patient is defined as prematurely censored if they had not progressed and the latest scan prior to DCO was more than one scheduled tumour assessment interval (+ 2 weeks) prior to the DCO date.

As patients will be randomised, imbalances in demographic factors between the treatment groups are not anticipated. However if any imbalances should occur, the HR and associated confidence interval calculated from a Cox Proportional Hazards model containing treatment, stratification variables and these additional demographic variables, may be reported.

Subgroup analyses will be conducted comparing PFS between treatments. The purpose of the subgroup analyses is to assess the consistency of treatment effect across potential or expected prognostic factors. If there are too few events available for a meaningful analysis of a particular subgroup (it is not considered appropriate to present analyses where there are less than 20 events in a subgroup), the relationship between that subgroup and PFS will not be formally analysed. In this case, only descriptive summaries will be provided

The following subgroups of the full analysis set will be analysed for PFS

Stratification factors

- Received prior chemotherapy regimens for metastatic breast cancer (yes/no)
- ER and/or PgR positive vs ER and PgR negative
- Prior platinum for breast cancer (yes/no)

Additional subgroups of interest include:

- Progressive disease at time of randomisation (yes/no)

- Measurable versus non measurable disease
- *BRCA* mutation type, e.g. *BRCA1*, *BRCA2* or *BRCA1/2* (both)
- Age at randomisation
- Region
- Race

Other baseline variables may also be assessed if there is clinical justification.

For each subgroup, the HRs (olaparib: physician's choice of chemotherapy) and associated CIs will be calculated from a Cox proportional hazards model (ties = Efron) that contains the treatment term, factor and treatment-by-factor interaction term. The treatment effect HRs for each treatment comparison along with their confidence intervals will be obtained for each level of the subgroup from this single model. The HRs and 95% CIs will be presented on a forest plot including the HR and 95% CI from the overall population (using the primary analysis).

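### The QoL mixed model leaves out the three randomisation factors, so its 95% CI is valid but slightly too wide if they predict QoL; a lesser mismatch affects the subgroup forest plot

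*Protocol*

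**What the plan says.** Section 5.2.1 states: "The randomisation scheme will be stratified based on" prior chemotherapy for metastatic disease, hormone receptor status and prior platinum for breast cancer. Section 12.2.2 carries these into the primary analysis: "PFS will be analysed using a log rank test stratified by the stratification factors". Sections 12.2.3.1 and 12.2.3.2 apply the same methodology to PFS2 and OS.

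The QoL model in section 12.2.3.4 is fully listed: "The model will include treatment, visit and treatment by visit interaction as explanatory variables and the baseline QoL score as a covariate". Its overall comparison is to be "presented along with an estimate of the treatment difference, 95% confidence interval and p-value". It serves secondary objective 2 and appears in Table 10 among the formal statistical analyses.

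For subgroups, section 12.2.2 specifies a Cox model that "contains the treatment term, factor and treatment-by-factor interaction term". The resulting HRs go on a forest plot with the overall HR from the primary analysis, which is exp(U/V) from the stratified log-rank test. Elsewhere in the same section, the Cox model for demographic imbalance and the global interaction model both include the stratification factors.

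**The concern.** Stratified randomisation balances the arms within strata, so between-stratum differences contribute almost nothing to the sampling error of the treatment contrast. A model without the strata still counts that variation as residual noise. Its standard error is then larger than the true sampling variability, and the interval is wider than it needs to be. The protocol writes out the model terms, so this is a choice already made and not one left to the SAP.

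It is plausible that the factors carry information. Section 1.1.1 names hormone receptor status as a baseline prognostic factor, and section 12.2.2 lists all three factors among subgroups chosen as potentially or expectedly prognostic. That refers to disease outcome, however. The protocol gives no figure linking any of them to QoL.

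The forest plot is meant to show whether the effect is consistent. Its rows and its reference line come from models that differ in adjustment and in estimator, so a reader could take a technical offset for a weaker effect in the subgroups.

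**Working it through.** **The plan's own figure.** Events for 90% power at HR 0.635, two-sided 5%, 2:1: (1.960 + 1.282)² / [(2/3)(1/3)(ln 0.635)²] = 10.51 / (0.2222 × 0.2062) ≈ 229.3, so 230 as stated in section 12.3 (power at 230 events: 0.901). This confirms the design inputs but does not bear on the point.

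**QoL model.** Let R² be the share of residual variance, after baseline QoL, that the three factors explain. The ratio of the planned CI width to the width with the factors included is 1/√(1 − R²). The protocol gives no R², so a range is assumed.

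| R² (assumed) | Width ratio | Planned CI too wide by |
|---|---|---|
| 0% | 1.000 | 0% |
| 1% | 1.005 | 0.5% |
| 2% | 1.010 | 1.0% |
| 5% | 1.026 | 2.6% |
| 10% | 1.054 | 5.4% |

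A simulation agrees. It used 4,000 single-score ANCOVAs per setting as a stand-in for the mixed model, with 310 patients and stratified 2:1 blocks of three (block size assumed). At R² of 5%, the unadjusted model SE was 2.41 against a true SD of 2.33, with coverage 95.9%. At 10% it was 2.41 against 2.30, with coverage 96.3%. Coverage with the factors included was about 95%.

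**Forest plot: the estimator.** With no prognostic factors and a proportion p of the risk set on olaparib, expected U divided by V at an event is (θ − 1)/(pθ + 1 − p).
- At entry, p = 2/3 and θ = 0.635: −0.365/0.7567 = −0.482, and exp(−0.482) = 0.617.
- At 4 months, with the assumed 4-month control median, 50% of control and 2^(−0.635) = 64.4% of olaparib patients remain event-free. So p = 1.288/1.788 = 0.72, and −0.365/0.7372 = −0.495, giving 0.610.

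So exp(U/V) settles near 0.61 when the HR is 0.635, whether or not the factors matter.

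**Forest plot: the omitted factors.** A large-sample simulation used 300,000 patients, exponential PFS, HR 0.635, 2:1 allocation, 22-month recruitment and a 27-month cut-off. Factor prevalences of 0.7, 0.5 and 0.3, the dropout rate and the prognostic HRs are assumptions; simulated maturity was 65% to 71%.

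| Prognostic HR per factor | Adjusted Cox | Stratified exp(U/V), the planned overall HR | Planned subgroup model, other factor | Planned subgroup model, stratification factor |
|---|---|---|---|---|
| 1.0 | 0.635 | 0.609 | 0.635 | 0.635 |
| 1.2 | 0.641 | 0.616 | 0.645 | 0.644 |
| 1.5 | 0.636 | 0.610 | 0.653 | 0.647 |
| 2.0 | 0.632 | 0.606 | 0.671 | 0.659 |

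- Estimator gap (adjusted Cox minus exp(U/V)): 0.026, 0.025, 0.026, 0.026.
- Shift from omission (other-factor subgroup minus adjusted Cox): 0, 0.004, 0.017, 0.039.
- Both push the same way, so subgroup rows sit closer to 1 than the reference by 0.026, 0.029, 0.043 and 0.065.

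**Against subgroup precision.** SE of log HR is √[9/(2d)] for d events at 2:1: 0.198 at 115 events (half of 230) and 0.474 at the 20-event minimum in section 12.2.2. The omission shift at a prognostic HR of 1.5 is ln(0.653/0.636) = 0.026, or 0.13 SE and 0.06 SE. At 2.0 it is ln(0.671/0.632) = 0.060, or 0.30 SE and 0.13 SE.

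**The case against.** The strongest reply is that little depends on this. QoL is outside the multiple testing procedure of section 12.2.1, the model already adjusts for baseline QoL, and any error is on the safe side. Section 12.2.3.4 also calls the data descriptive. The subgroup analyses are declared exploratory, and the global interaction test, which does include the stratification factors, is the formal check of consistency. All of this stands and limits the weight of the point. It does not remove it, because the QoL model still yields a difference, CI and p-value, and the correction is nearly free.

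Three stronger readings are tempting but not supported:
- A reader might infer that the QoL interval is invalid. It is not: coverage is at or slightly above 95%, and the excess width exists only if the factors predict QoL beyond baseline.
- A reader might infer that all subgroup models ignore all three factors, and that this alone makes subgroups look weaker than the overall result. Three of the nine listed subgroups are stratification factors, so those models contain one of them. At prognostic HRs of 1.2 and 1.5 the estimator gap (about 0.025) exceeds the omission shift (0.004 and 0.017). Stratifying the subgroup models alone would still leave about 0.635 plotted beside about 0.61.
- A reader might infer bias in QoL because questionnaires stop at progression and the factors may predict progression. Including them could make a missing-at-random assumption more plausible, but no figure in the protocol links them to QoL and no bias has been shown.

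**Conclusion.** The point holds in a limited form. The QoL model omits the factors that the trial randomises by and uses for its time-to-event analyses. The result is a valid but conservative interval, 0.5% to 5.4% too wide for an assumed R² of 1% to 10%, with no difference at 0%.

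The forest-plot point is secondary and minor. Rows and reference differ by about 0.025 from the estimator under 2:1 allocation, plus about 0.01 to 0.04 from omitted factors if these are moderately to strongly prognostic (0.004 at a prognostic HR of 1.2). The omission part is small against the precision of any subgroup. These sizes rest on assumed prognostic effects and prevalences; the estimator gap does not need the factors to be prognostic. Type I error control for PFS, PFS2 and OS is untouched.

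**What to change.** In section 12.2.3.4, add the three stratification factors as fixed effects in the QoL mixed model, using IVRS/IWRS values as the primary analysis does. The data are already held, and the cost is three degrees of freedom and a wording change.

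For the forest plot in section 12.2.2, show an overall HR from a Cox model of the same type as the subgroup models. Adjust or stratify both by the randomisation factors, leaving out whichever is the subgroup factor, where event numbers allow. The primary-analysis HR can still be reported in its own place. In simulation for the whole trial, stratifying raised the SE of log HR from 0.138 to 0.142. The loss in small subgroups was not measured, so covariate adjustment, or no adjustment, should be allowed where strata are sparse.
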